The primary substance abuse outcomes (self-reported abstinence) will be assessed throughout the study and through a six month follow-up. Additional outcomes will include use of other services (medical, legal), patient and provider satisfaction, as well as the costs of implementing the program. Each week, the counsellors will deliver a questionnaire (provided by the CHCR) which covers this range of topics to their patient participating in the trial. The data will be analyzed with a focus on feasibility (retention in both conditions, levels of substance abuse, health problems, and cost by condition).

4. SUBJECT SELECTION:

Participants will be recruited from Prince Edward Island; Lennox Island Health Centre and Abegweit Health Centre, Mount Herbert Provincial Addictions Treatment Facility Transition Unit and Methadone clinic, Holland College Student Services, University of Prince Edward Island Student Services, Charlottetown Methadone Clinic and Prince County Hospital. At RECAP in New Brunswick and Ontario Shores Mental Health Centre in Ontario.

A total of 240 Participants will be recruited during years 1-2 and an additional 440 participants will be recruited during years 3-4 ending in April 2019.

Counsellors already employed by the Centres will recruit participants who are willing to consent to a randomized trial of CBT4CBT. In order to create as representative a sample as possible, the inclusion criteria will be fairly broad, including any consenting individual who reports substance abuse in the past thirty days. Individuals who are currently suicidal, homicidal, or require immediate hospitalization will be excluded.

The participants will be patients who have reported substance abuse in the past thirty days. For the initial trial, all participating individuals will be over eighteen years of age and be approved to participate by their addictions counsellors.

Counsellors will ask individuals seeking treatment for substance abuse if they would be interested in learning about and participating in a substance abuse treatment project. If yes, participants will be introduced to the study Research Assistant who will go through the consent form(attached) with them. The Research Assistant will orally read the forms if necessary and individuals will be informed of their right to withdraw from the program should the need arise.

5. RESEARCH PLAN:

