The individuals recruited for this study will each fall into one or more subgroup of the trial (transitioning patients [inpatient to outpatient], youth [18-24 years], maintained on methadone, and indigenous individuals) and will be analyzed individually as well as collectively by compiling results from all sites. A subgroup analysis based on gender is also planned to investigate any differences in outcomes between male and female participants, these two groups, historically, can show significant differences in response to mental health and addictions treatment.

Participants will be randomized to either test or control groups. Participants in the control group will receive treatment as usual (the conventional treatment offered at that site) and will also meet with the Research Assistant during week 4 and week 8 to complete questionnaires (attached) either in hard copy or online on a tablet provided. These participants will also be contacted six months after their eight-week participation in the trial ended to complete a follow-up questionnaire.

Participants randomized to the test group will receive treatment as usual but will also be asked to spend at least thirty minutes per week using the program. CBT4CBT use by each participant will be monitored throughout the trial to ensure that this requirement is being met. They may choose to do this on location at the site or from their personal computer/tablet. The individuals in this arm of the trial will also meet with a Research Assistant once a week for eight weeks to complete questionnaires and will be contacted six months after their eight-week participation in the trial ended to complete a follow-up questionnaire. These questionnaires can be completed online. Each participant will be asked to participate in the eight-week long treatment period regardless of group (test or control). In addition to participants' treatment as usual, this will involve a

commitment of approximately 10 minutes as a weekly average from participants in the control group, and approximately 45 minutes as a weekly average from participants in the test group. Please see the consent form table outlining the time commitments in more detail.

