This trial design will mirror the designs in the trials already successfully conducted in the United States. Once an individual consents to participate, the counsellor will contact the Research Assistant who will meet with the individual and assign them a participant number generated using Randomizer.org (Geoffrey C. Urbaniak, 2015). This number will have been previously assigned to either test or control. The participant will be notified about the trial arm that they are placed into so that their participation may commence.

A Research Assistant will deliver the questionnaires to the trial participants. Questionnaires may be answered in hard copy or online in private. This removes the pressure from the participants to 'improve' in the eyes of their counsellor. Other than the addition of sections specifically relating to the CBT4CBT program, the questionnaires between groups will be identical.

As mentioned above, three previous/pilot studies in urban areas of the U.S. have been performed ([name] et al., 2008, 2009, 2014). The trial described herein will follow a very similar design.

Questionnaires, data analysis and protocols are based on those previously used by our collaborator in the US and have all been tailored to better suit Canadian populations. Based on the significant success that [name] had using these outcomes, tools and protocols we are confident in their reliability and validity.

Individuals who consent to this trial will be notified at the beginning of the trial that they have the right to remove themselves from the trial at any time. They also have the right to contact their counsellor or either co-investigator (phone numbers and emails provided on the consent form) at any time should they have questions or concerns. The counsellors also hold the ability to remove any of their patients from the trial at any time if they see fit.

6. ANALYSIS OF DATA:

Statistical analysis techniques previously used by the Co-Investigator [name] and her team will be performed on the generated data from this trial ([name] et al., 2008, 2009, 2014). These include one and two-way analysis of variance (ANOVA's) where appropriate. This will ensure a relevant analysis approach is used for the field of addictions treatment research as well as ensuring that the generated results may be compared with those previously established at other sites.

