The power calculations performed to calculate the sample size are based on three similar published trials of CBT4CBT in urban populations in the US. Primary outcome measurements of this trial will be a subset of measurements collected in these previous trials. We believe retention and follow up rates will be similar if not higher than the previous trials as PEI has a less transient community than most urban centers like Connecticut. Based on the three previous trials ([name] et al., 2008, 2009, 2014), the average drug use measurement (measured by the percent days abstinence from all drugs) in the test groups was 75% and control group 66% with a common standard deviation of 24% at the end of the eight week trial. Retention during the eight week trial was on average 77% and follow-up success was approximately 87% six months post trial. These values were used to calculate the sample size of 30 (for each group) to achieve statistical significance with an alpha of 0.5 and a power of 0.8 for subgroup analysis of the initial trials on PEI, and an alpha 0.05 and a power of 0.8 for combined analysis (i.e. combining results from

all 240 participants across the four trial settings). Power calculations to achieve statistical significance with an alpha of 0.05 and a power of 0.9 were calculated for the large-scale effectiveness trials and a sample size of 110 was found.

Primary outcomes measured include retention, changes in drug use, changes in health (e.g. medical visits, family and social satisfaction, etc.) and program implementation costs. The outcomes to be determined are identical in the four parallel trials to foster comparability across populations.

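### Abstinence is recorded repeatedly, but section 6 names only one- and two-way ANOVA and does not say which time point is tested or how repeated records are handled

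*Combined protocol and SAP*

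**What the plan says.** All references are to the combined protocol and SAP.

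- **Outcome (section 3).** "The primary substance abuse outcomes (self-reported abstinence) will be assessed throughout the study and through a six month follow-up".
- **Schedule (section 5).** Control participants "will also meet with the Research Assistant during week 4 and week 8 to complete questionnaires". Test participants "will also meet with a Research Assistant once a week for eight weeks to complete questionnaires". Both arms are contacted again six months after the eight-week period. That makes three records per control participant and nine per test participant; week 4, week 8 and six months are common to both arms.
- **Method (section 6).** The data are to be analysed with "Statistical analysis techniques previously used by the Co-Investigator" and team in three cited trials. Of these, "These include one and two-way analysis of variance (ANOVA's) where appropriate". No other quantitative test is named.
- **Sizing (section 6).** Mean percent days abstinent "in the test groups was 75% and control group 66% with a common standard deviation of 24% at the end of the eight week trial". This is one value per person.

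Week 8 is used for sizing but is not named as the time point of the primary analysis. No participant term, mixed model or within-person correlation is given.

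**The concern.** Participants are randomised, so the participant is the unit on which the arms can be compared. Several abstinence values from one person are correlated, and ordinary one- or two-way ANOVA has no term for that. The plan therefore leaves two routes open, each with a weakness.

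1. *One value per person at week 8.* The test is valid, but people without a week-8 value drop out of it, and the other assessments are not used.
2. *Arm-by-time ANOVA on all records.* Each questionnaire is counted as if it came from a separate person. The standard error of the arm effect is then too small, and chance differences are declared significant too often. The arm-by-time test errs the other way, because its error term wrongly includes between-person variation.

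The second problem arises even with complete data and a single test, so it is separate from missing data and from multiple testing. At stake is whether the main result can be trusted: section 7 aims for the program to become a standard option across Canada, and section 8 makes later access for controls depend on verified benefit.

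**Working it through.** **Inputs.** From section 6: 75% versus 66% (difference 9 points), SD 24, alpha 0.05 and power 0.8 for the combined analysis, 240 participants, retention 77%. From section 5: three control and nine test records, three visits shared. Assumed: 1:1 allocation (120 per arm), two-sided tests, and an equal correlation rho between any two values from one person. The plan gives no rho, so 0.3, 0.5 and 0.7 are shown.

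**Step 1: the plan's own sizing.** n per arm = 2 × (1.96 + 0.84)² × 24² / 9² ≈ 112. Power at n per arm is Φ(9 / (24 × √(2/n)) − 1.96). At 120 this is Φ(2.90 − 1.96) = 82.8%. So 240 is sufficient before dropout, for a single week-8 value per person. The other printed sizes do not reproduce: 30 per group at alpha 0.5 (33 needed), and 110 at power 0.9 (150 per arm needed). Those are separate matters and do not bear on this point. The plan states no error rate for repeated records, so there is none to reproduce.

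**Step 2: one week-8 value per person.** Simulated error rate of the arm test at 120 per arm: 4.7%, so the test is sound. If 77% retention means 77% supply a week-8 value, 120 × 0.77 ≈ 92 per arm remain, and power is Φ(2.54 − 1.96) = 72.0%.

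**Step 3: k records per person in each arm, treated as independent.** The true variance of the arm difference is 1 + (k − 1)rho times the variance the ANOVA assumes, so the error rate is 2 × [1 − Φ(1.96 / √(1 + (k − 1)rho))]. For k = 3 and rho = 0.5 the factor is 2, and 1.96 / √2 = 1.386, which gives 16.6%.

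**Step 4: all nine test and three control records pooled in an arm comparison.** The factor is [(1 + 8rho)/9 + (1 + 2rho)/3] / (1/9 + 1/3). At rho = 0.5 this is (0.556 + 0.667) / 0.444 = 2.75, and 1.96 / √2.75 = 1.182, which gives 23.7%.

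| Records entered as independent | rho 0.3 | rho 0.5 | rho 0.7 |
|---|---|---|---|
| Weeks 4 and 8, both arms | 8.6% | 11.0% | 13.3% |
| Three shared visits, both arms | 12.1% | 16.6% | 20.6% |
| Nine test, three control | 17.1% | 23.7% | 29.1% |

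Simulation (20,000 runs per setting) agrees for three shared visits: two-way ANOVA at 120 per arm rejects in 12.5%, 16.4% and 20.8%. At rho 0.5 the rate is much the same at 30 per arm (16.2%), so it does not depend on sample size.

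**Step 5: the arm-by-time test.** With three visits, its large-sample error rate is 0.05 raised to the power 1/(1 − rho). At rho = 0.5 that is 0.05² = 0.0025 instead of 0.05: too strict, at the expense of power to detect a difference in course.

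**The case against.** The plan never says it will pool questionnaires. Its list of methods is open-ended and conditional, and two-way ANOVA may mean arm by site, gender or subgroup, all of which section 5 describes and all of which can use one value per person. Percent days abstinent is itself a within-person summary and can absorb repeated reports into one number; a change score also yields one value. The earlier trials' methods, adopted by reference, may include a repeated-measures analysis that cannot be seen here. Naming week-8 percent days abstinent as the tested value would remove the error-rate problem with the ANOVA already listed.

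Most of this stands. A reader might infer that the arm test in this trial runs at about 16% instead of 5%. The documents do not support that: the figure needs pooling, three records in both arms and a correlation near 0.5, none of which the plan states. Nor do they show that the intended analysis lacks a method for correlation, only that the text names none.

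What remains is that the tested time point and the handling of repeated records are left open, and that naming week 8 alone would still discard people without that value. The 23% figure has its own limit: retention may mean staying in treatment and not supplying data, and the plan's six-month follow-up rate of about 87% is higher than its retention rate.

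**Conclusion.** The point holds as an under-specified analysis that can be improved cheaply, not as a demonstrated wrong one. The one-value-per-person route keeps 5%, but on the plan's own retention figure could leave about 92 of 120 per arm and 72% power. The pooled route, permitted but not planned, would exceed 5% at any positive correlation: about 12% to 21% with three records per person, and 17% to 29% with nine versus three, for rho from 0.3 to 0.7. These ranges rest on equal correlation between visits and complete data. How much power a better model would recover cannot be worked out from the documents, since it depends on rho and on who attends week 4 and six months. The change should be made before data are analysed; it does not call the design into question.

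**What to change.** In section 6:

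- Analyse percent days abstinent with a mixed model for repeated measures on week 4, week 8 and six months, with arm, visit and arm-by-visit terms and an unstructured within-participant covariance.
- Name the week-8 test-minus-control contrast, the quantity used for sizing, as the primary treatment effect.
- State which days each visit's value covers, so that values do not overlap. Do not enter the test arm's extra weekly questionnaires as further records in this model.
- Keep ANOVA for analyses with one value per participant, and state that several questionnaires from one person will not be entered as independent observations.

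The model uses the week-4 and six-month values of people with no week-8 value, on the assumption that data are missing at random given what was observed. Three visits need only six covariance parameters (three variances and three covariances).

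Cost: one paragraph and standard software; no new visits, data or participants. Results become slightly less directly comparable with the earlier trials, which is the reason section 6 gives for its choice of methods. A supplementary one-way ANOVA on week-8 values meets that.

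### The PEI subgroup analyses are sized at an alpha of 0.5; at two-sided 0.05, 30 per arm gives power of about 0.30, not 0.8

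*Combined protocol and SAP*

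**What the plan says.** Section 6 (Analysis of Data) takes its planning values from three earlier trials: mean percent days abstinent of 75% on test and 66% on control, common SD 24% at the end of eight weeks, retention 77% during the trial, and follow-up 87% at six months. It continues: "These values were used to calculate the sample size of 30 (for each group", and gives the purpose as "to achieve statistical significance with an alpha of 0.5 and a power of 0.8 for subgroup analysis of the initial trials on PEI". The same sentence uses alpha 0.05 and power 0.8 for the combined analysis of "all 240 participants across the four trial settings".

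Section 5 (Research Plan) says that the subgroups (transitioning patients, youth, methadone-maintained and indigenous participants) "will be analyzed individually as well as collectively by compiling results from all sites". The planned methods in section 6 are ANOVAs: "These include one and two-way analysis of variance (ANOVA's) where appropriate". Sidedness is not stated. No other place sets a significance level for the subgroup analyses or gives a reason for 0.5. Section 3 adds: "The data will be analyzed with a focus on feasibility".

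**The concern.** An alpha of 0.5 means that a treatment with no effect would be declared effective or harmful in half of all tests. The obvious thought is that a zero was dropped from 0.05, particularly as 0.05 appears later in the same sentence. But 30 per arm looks far too few for 80% power at 0.05 with a standardised effect of 0.375, so correcting the misprint would leave a false power statement behind.

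The stakes differ by reading, and only one of the two can apply. If the subgroups are tested at 0.5, chance differences will be reported as effects in particular populations. If they are tested at 0.05, a real 9-point benefit will usually be missed while readers are told that power is 0.8. A null result in, say, the indigenous subgroup could then be taken to show that the program does not work there.

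**Working it through.** **Inputs (section 6).** Difference 75 − 66 = 9 points; SD 24; standardised effect d = 9/24 = 0.375; n = 30 per arm.

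**Assumptions.** Equal allocation. Two-sided testing as the main reading, because the F test of a two-arm ANOVA is equivalent to a two-sided t test; one-sided results are shown as well.

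**Method.** Two-sample t test, with power from the noncentral t distribution on 2n − 2 degrees of freedom and noncentrality d × √(n/2). At n = 30 the noncentrality is 0.375 × √15 = 1.452, and the standard error of the difference is 24 × √(2/30) = 6.20 points.

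**Step 1: reproduce the plan's figure at alpha 0.5.** The normal approximation, counting both tails, is

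Φ(1.452 − 0.674) + Φ(−1.452 − 0.674) = 0.782 + 0.017 = 0.798.

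The exact t calculation also gives 0.798. Solving for n gives 30.4 per arm, so 0.8 is reached by rounding (31 strictly). The two-sided alpha at which 30 per arm gives exactly 80% power is 0.504. One-sided 0.5 does not match: it needs about 10 per arm, and 30 per arm would give 0.93.

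**Step 2: consequence of testing at two-sided 0.5.** The false-positive rate is 50% per test. The critical observed difference is 0.679 × 6.20 = 4.2 points. In 200,000 simulated trials with no effect, 0.500 were rejected at alpha 0.5 and 0.050 at alpha 0.05. With a true 9-point effect the rates were 0.798 and 0.297.

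**Step 3: read 0.5 as 0.05.**

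| Alpha | Power at 30 per arm | n per arm for power 0.8 |
|---|---|---|
| Two-sided 0.5 | 0.798 | 30.4 |
| Two-sided 0.05 | 0.298 | 112.6 |
| One-sided 0.05 | 0.417 | 88.6 |

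The two-sided sample size can be checked by the normal formula: 2 × (1.960 + 0.842)² / 0.375² ≈ 112 per arm. With 30 per arm, the difference detectable with 80% power at two-sided 0.05 is 17.7 points, about twice the planned 9.

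**Step 4: loss and larger subgroups, two-sided 0.05.** If settings and arms are of equal size, 240 / 4 / 2 = 30, so 30 is the number enrolled per arm. The planning rates then leave 30 × 0.77 ≈ 23 or 30 × 0.87 ≈ 26. Sizes of 45 and 60 are assumed, to represent subgroups pooled across sites.

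| Analysed per arm | Power for 9 points | 95% CI half-width (points) |
|---|---|---|
| 23 | 0.24 | 14.3 |
| 26 | 0.26 | 13.4 |
| 30 | 0.30 | 12.4 |
| 45 | 0.42 | 10.1 |
| 60 | 0.53 | 8.7 |

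**Comparison.** The combined analysis is not affected: 120 per arm gives 0.82 at two-sided 0.05, before any loss.

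**The case against.** On the literal reading there is no arithmetic error, since 30 per arm and power 0.8 agree with alpha 0.5. The 0.5 also appears only in a sample-size sentence. Section 6 says the analysis follows the earlier trials, so the investigators may never have meant to judge results at 0.5. That is fair, but no other threshold is written down. If the intended one is 0.05, the power claim fails.

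The work is described as a pilot with a feasibility focus, the combined analysis uses 0.05, and tailoring of the program rests on qualitative feedback. This softens the consequence of low power. It does not justify stating 0.8 where the value is about 0.3, or sizing a test at 0.5.

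Three further points stand in part:

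- **Loss.** Section 6 says its listed values, which include retention and follow-up, were used to obtain 30. That sits awkwardly with the inference that 30 contains no allowance for loss, which depends on equal settings and equal allocation. If loss was counted and about 23 per arm are analysed, power at two-sided 0.5 is about 0.75. Also, 87% is a six-month rate while the effect is measured at eight weeks, so 0.24 and 0.26 are conditional illustrations.
- **Pooled subgroups.** If all 240 + 440 = 680 participants were split equally by gender and arm, there would be 170 per arm and power of 0.93. The low power concerns the PEI settings with about 30 per arm, and not every subgroup analysis in section 5.
- **The next sentence.** The figure of 110 for alpha 0.05 and power 0.9 does not reproduce either: power is 0.79 if 110 is per arm and about 0.50 if it is 55 per arm. This is a separate matter, but it is a reason to check which alpha was used throughout section 6.

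**Conclusion.** The concern holds, and the statement must be fixed. Either the subgroup alpha is literally 0.5, which makes each test a coin toss under no effect, or it is a misprint and the power is about 0.30 instead of 0.8. In the second case a true 9-point effect would be missed about 70% of the time with 30 analysed per arm.

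The close match of 30 per arm to two-sided 0.5 suggests that 0.5 entered the calculation, but the conclusion does not depend on this, because both readings are faulty. It rests on the plan's own effect and SD, equal allocation and a two-group comparison of means. One-sided testing at 0.05 raises power only to 0.42. The headline figures assume no loss; loss would lower them.

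**What to change.** In section 6, remove the alpha of 0.5 and replace the subgroup clause with wording to this effect:

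> Subgroup analyses use a two-sided alpha of 0.05. With 30 analysed per arm, power for a 9-point difference is about 0.30 (about 0.24 if 77% and 0.26 if 87% provide data), and the 95% confidence interval half-width is about 12 points (about 14 and 13 respectively). Where a subgroup pooled across sites has more than 30 per arm, power is given for its actual size. Subgroup results are reported as estimates with 95% confidence intervals, and a non-significant subgroup result is not read as absence of effect.

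While editing, the investigators should confirm which alpha was used for the other calculations in the section. The change supplies the significance level and reporting rule that the subgroup analyses now lack. It needs no added participants, visits or data. The cost is presentational: stated subgroup power falls from 0.8 to about 0.3, and the PEI subgroups can no longer be described as adequately powered.

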Participants in the 'test' group who respond well to CBT4CBT will have the opportunity to continue accessing the program at their leisure (using their provided login information) beyond the time frame of the study. Participants in the 'control' group may have the opportunity to access CBT4CBT once the trial is complete and assuming that positive effects of CBT4CBT are verified on PEI.

8. CONFIDENTIALITY:

The CHCR team currently work with Health PEI and the PEI Department of Health and Wellness on a CIHR-funded initiative which built the UPEI Secure Island Data Repository on the UPEI campus which holds de-identified PEI health records as well as any research-generated data from clinical trials such as this one. Therefore, the non-identifiable data generated

throughout this study will be stored, after collected and analysed, on secure servers in the UPEI Secure Data Facility. Only CHCR researchers (via password protection and key codes to the room) will have access to the data. All Data will be retained for a minimum of five years.

9. LIABILITY:

N/A

10. DISCLOSURE OF ANY FINANCIAL COMPENSATION:

N/A

11. REFERENCES:

Attached

12. APPENDICES:

Questionnaires or measuring instruments and appropriate copyright release (if applicable) should be included as appendices to the proposal when appropriate.

Any advertisements intended for use to recruit participants should be submitted for review.

Please see the General Guidelines (Section 3.11) concerning Advertisements.

Administrative Requirements for Research Protocols:

- Please use a font-size large enough to be legible (12pt Times New Roman font is preferred).
Protocols may be returned if this criterion is not met.
- Please include page numbers, as well as a version number and date on your proposal (which must be revised whenever the proposal is amended) and any appended data collection tools or measures.

Additional Considerations:

- Submissions based on a grant proposal (e.g. CIHR, PEI Research Fund), the level of data might not in all instances provide enough information about the methodology to meet the REB's requirements for ethical and scientific review. In these cases the grant proposal should be supplemented by further information based on the guidelines of the this REB.
- All documentation that will be provided to family doctors, participants, participant relatives and caregivers (including study introductory letters) must be reviewed and approved by the REB prior to use.

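### The 0.8 power stated for the combined 240-participant analysis holds, two-sided, only if about 94% are analysable at week 8; at the plan's quoted 87% it is about 77%

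*Combined protocol and SAP*

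**What the plan says.** Section 6 takes its assumptions from three earlier trials: 75% days abstinent in the test groups, 66% in the control groups, and a common SD of 24% at the end of eight weeks. It adds: "Retention during the eight week trial was on average 77% and follow-up success was approximately 87% six months post trial". It continues: "These values were used to calculate the sample size of 30 (for each group", and attaches to that 30 a printed alpha of 0.5 and power of 0.8 for the subgroup analyses. For the pooled comparison it states "an alpha 0.05 and a power of 0.8 for combined analysis", described as covering "all 240 participants across the four trial settings". Section 4 (Subject Selection) agrees on the number: "A total of 240 Participants will be recruited during years 1-2".

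On attrition in this trial, Section 6 says: "We believe retention and follow up rates will be similar if not higher than the previous trials". On method, the same section refers to the techniques of the earlier trials: "These include one and two-way analysis of variance". It does not say whether the test is one- or two-sided, shows no inflation for dropout, and gives no expected number analysable at week 8. The text supplied describes no method for missing data.

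**The concern.** The plan quotes two attrition-related rates and says they were used, yet the combined power appears to assume that nearly everyone recruited contributes a week-8 outcome. If so, the 0.8 is overstated at either quoted rate, and the sentence saying the rates were used is inaccurate.

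The combined comparison is the only one in the initial phase given a conventional alpha, so it carries whatever efficacy conclusion that phase can support. Section 7 (Risks and Benefits) makes possible later access for control participants conditional: "assuming that positive effects of CBT4CBT are verified on PEI". A false-negative result could therefore affect participants as well as the report. The weight is limited, because Section 3 puts the analytic focus on feasibility.

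**Working it through.** **Inputs**
- Difference 75 − 66 = 9 points and SD 24 at week 8 (Section 6), so d = 9/24 = 0.375.
- 240 participants. The ratio is not stated; 30 per group × 2 arms × 4 settings = 240 implies 1:1, or 120 per arm.
- Alpha 0.05 and stated power 0.8 (Section 6).
- Quoted rates: 77% retention over eight weeks and 87% follow-up at six months (Section 6).
- Assumption: two-sided test. With two arms, the F-test in a one-way analysis of variance is the two-sided t-test.

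**The plan's own figure.** With all 240 analysed, the two-sided noncentral t power at d = 0.375 and n = 120 per arm is 82.5% (normal approximation 82.8%). So 0.8 is met, with a small margin, if nobody is lost.

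**Number needed for 80%.** The normal approximation is n = 2(z₀.₉₇₅ + z₀.₈)²/d² = 2(1.960 + 0.842)²/0.375² = 111.6 per arm. The noncentral t gives 112.6. As a share of recruitment, 112.6/120 = 0.938, about 94% (93% by the normal approximation).

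**Power by share analysable (noncentral t, alpha 0.05)**

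| Share analysable | n per arm | Two-sided | One-sided |
|---|---|---|---|
| 100% | 120 | 82.5% | 89.5% |
| 94% | 112.6 | 80.0% | 87.7% |
| 90% | 108 | 78.3% | 86.5% |
| 87% | 104.4 | 76.9% | 85.4% |
| 77% | 92.4 | 71.8% | 81.4% |

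Two-sided, the chance of missing the planned effect is about 23% at 87% (100 − 76.9) and 28% at 77% (100 − 71.8), against the stated 20%.

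**Which reading fits the plan's other figure?** The 30 per group, at the alpha of 0.5 as printed, can be tested against each reading:
- Two-sided, no loss: n for 80% power is 30.4, and power at 30 is 79.8%. (This counts rejection in either direction; a normal approximation using one tail gives 33.)
- Two-sided with loss: 77.2% at 87% and 75.0% at 77%. Allowing for those losses would take 30.4/0.87 = 35 or 30.4/0.77 = 40 per group.
- One-sided: n for 80% power is 10.1, and power at 30 is 92.7%.
- If 0.5 is a misprint for 0.05, power at 30 is about 30% two-sided or 42% one-sided, so neither gives 0.8.

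Only a two-sided calculation with no attrition allowance reproduces the 30.

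**The case against.** The strongest objection is sidedness. A one-sided 0.05 test needs 88.6 per arm; allowing for 77% retention, 88.6/0.77 = 115, close to the 120 recruited, and power is 81.4%. On that reading the stated 0.8 is met and the sentence about using the retention rate could be true. This cannot be excluded, because the plan is silent. But the same reading fails for the 30 per group, where about 10 would have been enough, and it does not sit naturally with an analysis of variance. The third sample size in Section 6 (110, alpha 0.05, power 0.9) does not settle the matter: taken as per arm, 90% power needs 150 two-sided or 122 one-sided.

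Second, neither rate is week-8 evaluability: 77% is retention and 87% is follow-up at six months. This stands. Because follow-up exceeds retention, some people who left treatment were evidently still assessed, so 77% is a worst case. The plan also allows for rates above those in the earlier trials, but reaching 0.8 needs about 94%, and the plan does not claim that.

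Third, three points is small beside the uncertainty in the effect and SD. A two-way analysis might also recover it: if a second factor explained 8% of outcome variance (an illustrative assumption), power at 87% would be 80.3%, though still only 75.3% at 77%. It is fair to call the gap modest. The plan does not claim such a gain.

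Fourth, Section 7 offers control access only as a possibility and does not tie it to a significance test. That limits the consequence but does not support the stated power.

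**Conclusion.** The concern holds. With the plan's effect and SD, 1:1 allocation and a two-sided 0.05 test, the stated 0.8 is not delivered at either rate the plan quotes. The size is modest: about 3 points short if 87% are analysable, and about 8 if every treatment dropout also lacks the week-8 outcome. The arithmetic is firm. Confidence is medium because two-sidedness is an inference and the analysable share is unknown; under a one-sided 0.05 test, or with at least about 94% analysable, there is no shortfall. On any reading, sidedness, the analysable number and the role of the 77% and 87% need to be stated.

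**What to change.** In Section 6:
1. State that the combined comparison is two-sided. If a one-sided test was intended, say so and justify it.
2. Give the expected number per arm with an analysable week-8 outcome.
3. For a two-sided test, restate the combined power as about 77% with 87% analysable, falling to about 72% with 77%. If better capture than in the earlier trials is expected, say that 0.8 requires about 94%, or 113 per arm.
4. Show how the 77% and 87% entered the calculation, or correct the sentence that says they did.

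The cost is wording only, with no change to enrolment, visits or data collection. The stated power becomes slightly less favourable.
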